6.1.2 Noninvestigational Products/Auxiliary Medicinal Products

After the occurrence of an event that, in the opinion of the investigator, warrants other treatment, supportive care should be provided including, but not limited to, the guidance in [Table 6-2](#) for Dose Modification Guidelines for Adverse Events.

6.1.2.1 Pre- and Post-infusion Medications

Dexamethasone

Dexamethasone 8 mg IV (or equivalent dose of other corticosteroids) will be administered within 1 hour prior to tarlatamab infusion on C1D1 and C1D8.

IV Hydration

Intravenous hydration (1 L normal saline) over 2 to 4 hours following tarlatamab administration on C1D1 and C1D8.

6.1.2.2 Cytokine Release Syndrome Rescue Medication

All sites will ensure that CRS rescue medications are available on-site, including corticosteroids and sites are required to have tocilizumab or siltuximab (if tocilizumab is not available) on site for potential treatment of CRS.

6.1.3 Medical Devices

Non-investigational medical devices may be used in the conduct of this study as part of standard care.

Non-Amgen noninvestigational medical devices (eg, syringes, sterile needles), that are commercially available are not usually provided or reimbursed by Amgen (except, for example, if required by local regulation). The investigator will be responsible for obtaining supplies of these devices.

6.1.4 Other Intervention Procedures

There are no other intervention procedures in this study.

6.1.5 Product Complaints

A product complaint is any written, electronic, or oral communication that alleges deficiencies related to the identity, quality, durability, reliability, safety, effectiveness, or performance of a drug, combination product, or device after it is released for distribution to market or clinic by either (1) Amgen or (2) distributors or partners for whom Amgen manufactures the material. This includes all components distributed with the drug, such as packaging drug containers, delivery systems, labeling, and inserts.

This includes any investigational product and/or other non-investigational product(s)/auxiliary medicinal product(s) provisioned and/or repackaged/modified by Amgen:

- tarlatamab

Any product complaint(s) associated with an investigational product and/or noninvestigational product(s)/auxiliary medicinal product(s) supplied by Amgen are to be reported.

6.1.6 Excluded Treatments, Medical Devices, and/or Procedures During Study Period

The following treatments and/or procedures are excluded within the timeframes specified during the study:

- Other investigational agents, devices (other than those specified in the protocol) and procedures are prohibited while on study treatment.
- Anticancer therapies other than those specified in the protocol are prohibited while on study treatment.
- Radiation therapy
 - Exception: Radiation therapy for symptom control (eg, bone metastasis) or brain metastasis treatment may be allowed after discussion with the medical monitor. The radiation therapy should not include the thoracic field and must have been completed at least 7 days before the subsequent dose of tarlatamab.
- Immunosuppressive agents with the exception of those required by protocol, treatment for adverse events, CNS metastases, corticosteroid replacement therapy, or unless agreed upon by the investigator and medical monitor.
- During tarlatamab treatment: Live and live-attenuated vaccines are prohibited for the duration of tarlatamab treatment.
 - Live viral non-replicating vaccine (eg, Jynneos for mpox infection) is allowed when administered > 3 days before or > 3 days after a tarlatamab infusion.
 - Seasonal influenza vaccines for injection are generally killed virus vaccines and are allowed when administered > 3 days before or > 3 days after a tarlatamab infusion. However, intranasal influenza vaccines (eg, Flu - Mist®) are live-attenuated vaccines, and are not allowed at any time during tarlatamab treatment.
 - Vaccinations for coronavirus disease 2019 ([COVID-19], severe acute respiratory syndrome coronavirus 2 [SARS-CoV-2] vaccination) are generally not live or live-attenuated and are allowed when administered > 3 days before or > 3 days after a tarlatamab infusion.
 - After completion of tarlatamab treatment: live and live-attenuated vaccines are prohibited for a further **60** (+5) days after the last dose of tarlatamab.
- Subjects must not schedule any major elective surgery during the treatment period and for at least 30 days after the last administration of study treatment. If a subject undergoes any unexpected surgery during the course of the study, all study

treatments must be withheld, and the investigator or designee should notify the sponsor's medical monitor as soon as possible. A subject may be allowed to resume study drugs if both the investigator and sponsor's medical monitor agree to restart study therapy.

6.1.7 Continuation on Investigational Product Treatment After First Radiologic Disease Progression

This section details the conditions necessary to allow continued study treatment after first disease progression in subjects that, in the investigator's judgment, continue to have clinical benefit. All of the following criteria must be met:

- Subject continues to have clinical benefit per the investigator's judgment.
- Subject has stable ECOG PS.
- Absence of threat to vital organs or critical anatomical sites (eg, respiratory failure due to tumor compression, spinal cord compression) requiring urgent alternative medical intervention with persistent immediate threat to vital organs after intervention. The presence of brain metastases is allowed provided the lesions are amenable to radiation therapy or dexamethasone (or corticosteroid equivalent), and the subject is clinically stable in the investigator's judgment.
- Subject continues to tolerate study drug.
- No other treatment discontinuation criteria are met ([Table 6-2](#) and **Section 11.7.1**).
- No significant, unacceptable, or irreversible toxicities related to any dose of the study treatment or treatment-related adverse events of Common Terminology Criteria for Adverse Events (CTCAE) grade 3 at the current dose at the time of progression.
- Radiation therapy is permitted after discussion with the medical monitor. Palliative radiation and/or surgery for new, progressive, or symptomatic lesions is permitted. Study treatment must be held during either treatment (radiation and/or surgery) and the treatment must be completed at least 7 days before the subsequent dose of study treatment.

Subjects should continue to perform all protocol-required procedures as noted in the Schedule of Activities (Section [1.3](#); imaging, labs, and clinic visits).

Any subsequent (investigator determined) progressive disease per RECIST 1.1 from a new baseline set at initial progression will result in permanent discontinuation of study treatment.

6.2 Dose Modification

6.2.1 Dose-group Study Escalation/De-escalation and Stopping Rules

Not applicable.

6.2.2 Dosage Adjustments, Delays, Rules for Withholding or Restarting, Permanent Discontinuation

6.2.2.1 Amgen Investigational Product: Tarlatamab

The reason for dose change of tarlatamab is to be recorded on each subject's CRF(s).

Tarlatamab will be discontinued or temporarily delayed in the event of a toxicity that, in the opinion of the investigator, warrants the discontinuation or dose delay. For treatment interruptions, delays, and discontinuations, refer to tarlatamab guidance in [Table 6-2](#).

Table 6-2. Tarlatamab Dose Modification Guidelines for Adverse Events

Grade	Description of Severity	Interruption/Delay	Specific Management	Restart guidance	Permanent Discontinuation
Neurologic Events					
1	Reference Section 11.11.2 for grading and management guidelines	No additional guidance	Follow institutional guidelines for management and per local practice: 
 Consider diagnostic workup for alternate diagnosis^a Supportive Care 	No additional guidance	No additional guidance
2		No additional guidance	Follow institutional guidelines for management and administer corticosteroids per local practice: 
 Consider diagnostic workup for alternate diagnosis^a Reference dose of corticosteroids for grade 2 ICANS ^a : 
 Dexamethasone 8 mg to 10 mg IV every 12 hours or methylprednisolone equivalent. Once ICANS improves to grade 1 or less, taper and/or stop corticosteroids depending on clinical situation 	No additional guidance	No additional guidance
3		Delay tarlatamab until the event improves to grade ≤ 1	Follow institutional guidelines for management and administer corticosteroids per local practice: 
 Consider diagnostic workup for alternate diagnosis^a Consider ICU transfer Reference dose of corticosteroids for grade 3 ICANS ^a : 
 Dexamethasone 10 mg IV every 6 hours or methylprednisolone equivalent (1 mg/kg IV every 12 hours). Once ICANS improves to grade 1 or less, taper and/or stop corticosteroids depending on clinical situation 	Resume tarlatamab no less than 72 hours after the initial observation of the grade 3 adverse event	
 Initial grade 3 neurologic event does not improve to grade ≤ 1 within 7 days, OR Grade 3 neurologic event reoccurs within 7 days of resuming tarlatamab

Abbreviations and footnotes defined on last page of table.

Table 6-2. Tarlatamab Dose Modification Guidelines for Adverse Events

Grade	Description of Severity	Interruption/Delay	Specific Management	Restart guidance	Permanent Discontinuation
Neurologic Events (continued)					
4	Reference Section 11.11.2 for grading and management guidelines	Immediately stop any ongoing infusion	Follow institutional guidelines for management and administer corticosteroids per local practice: 
 Consider diagnostic workup for alternate diagnosis^a Transfer to ICU Reference dose of corticosteroids for grade 4 ICANS ^a : 
 Methylprednisolone 1000 mg/day in divided doses IV for 3 days followed by taper as clinically indicated. Consider additional therapies per guidelines	Permanently discontinue	Permanently discontinue
Seizure		Delay tarlatamab until the event improves to grade ≤ 1	Administration of corticosteroids and anti-seizure medication is permissible based on investigator judgment and local practice.	Do not resume tarlatamab until 7 days after the last seizure and after therapeutic levels of anti-seizure medication are likely to have been achieved.	If a second seizure occurs after resuming tarlatamab

Abbreviations and footnotes defined on last page of table.

Table 6-2. Tarlatamab Dose Modification Guidelines for Adverse Events

Grade	Description of Severity ^b	Interruption/Delay	Specific Management	Restart guidance	Permanent Discontinuation
Cytokine Release Syndrome (see Section 11.11.1 for additional guidance and grading scale details)					
1	Symptoms are not life-threatening and require symptomatic treatment only 
 • Fever^c: $\geq 38^{\circ}\text{C}$ • Hypotension: none • Hypoxia: none 	No action required	Administer: 
 • Symptomatic treatment (eg, paracetamol/acetaminophen) for fever • Consider a single dose of dexamethasone (or equivalent) ranging from 4 mg to 10 mg Monitor: 
 • CRS symptoms including temperature, blood pressure, and pulse oximetry • Fluid status, maintain IVF as needed • Consider chest X-ray and obtaining appropriate cultures to rule out infection For subjects with rapid onset (< 4 hours from start of infusion), extensive co-morbidities or poor PS, strong suggestion to manage per grade 3 CRS guidance below.	No additional guidance	No additional guidance

Abbreviations and footnotes defined on last page of table.

Table 6-2. Tarlatamab Dose Modification Guidelines for Adverse Events

Grade	Description of Severity ^b	Interruption/Delay	Specific Management	Restart guidance	Permanent Discontinuation
Cytokine Release Syndrome continued (see Section 11.11.1 for additional guidance and grading scale details)					
2	
 Fever^c: $\geq 38^{\circ}\text{C}$ 
WITH
 
 Hypotension: not requiring vasopressors 
AND/OR^d
 
 Hypoxia: requiring low-flow nasal cannula^e or blow-by 	Delay tarlatamab until event improves to CRS grade ≤ 1 .	
Administer:
 
 Symptomatic treatment (eg, paracetamol/acetaminophen) for fever Consider a single dose of dexamethasone (or equivalent) ranging from 4 mg to 10 mg Supplemental oxygen when oxygen saturation is $< 90\%$ on room air (low-flow ≤ 6 L/minute] nasal cannula or blow-by) Intravenous fluids when systolic blood pressure is < 85 mmHg. Persistent tachycardia (eg, > 120 bpm) may also indicate the need for intervention for hypotension 
Monitor:
 
 CRS symptoms including temperature, blood pressure, and pulse oximetry Fluid status, maintain IVF as needed Cardiac and other organ function Consider chest X-ray and obtaining appropriate cultures to rule out infection 
For subjects with rapid onset (< 4 hours from start of infusion), extensive co-morbidities or poor performance status, strong suggestion to manage per grade 3 CRS guidance below.
	
 The next infusion may be administered if the event has resolved to grade ≤ 1 prior to resuming treatment In case of infusion interruption, continue treatment with next scheduled infusion. Do not resume prior infusion or administer delayed infusion. 	If there is no improvement to CRS \leq grade 1 within 7 days

Abbreviations and footnotes defined on last page of table.

Table 6-2. Tarlatamab Dose Modification Guidelines for Adverse Events

Grade	Description of Severity ^b	Interruption/Delay	Specific Management	Restart guidance	Permanent Discontinuation
Cytokine Release Syndrome continued (see Section 11.11.1 for additional guidance and grading scale details)					
3	
 Fever^c: $\geq 38^{\circ}\text{C}$ WITH Hypotension: requiring a single vasopressor (excluding vasopressin) AND/OR^d Hypoxia: requiring high-flow nasal cannula^e, facemask, nonrebreather mask, or Venturi mask 	Delay tarlatamab until event improves to CRS grade ≤ 1 .	
Administer:
 
 Symptomatic treatment (eg, paracetamol/acetaminophen) for fever Supplemental oxygen (high-flow nasal cannula [$> 6 \text{ L/min}$]), facemask, non-rebreather mask, or Venturi mask), as needed A vasopressor \pm vasopressin, as needed Dexamethasone (or equivalent) IV at a dose maximum of 3 doses of 8 mg (24 mg/d). The dose should then be reduced step-wise. 
AND/OR
 
 Consider use of tocilizumab (in countries where available) as an additional therapy in this setting at a dose of 4 to 8 mg/kg as a single dose. The maximum dose per infusion for tocilizumab is 800 mg. Tocilizumab can be repeated for an additional 3 doses with at least an 8-hour interval between doses. If tocilizumab is not available, siltuximab (an anti-IL-6 monoclonal antibody) may be used in the management of CRS, following the criteria outlined in this table. The recommended dose of siltuximab is 11 mg/kg administered over 1 hour as an IV infusion, consistent with the prescribing information for the treatment of multicentric Castleman's disease (Sylvant Prescribing Information), and the CARTOX Working Group Guidelines for CRS management (Neelapu et al, 2018). Siltuximab may be repeated if needed, in the event that CRS recurs after a subsequent infusion of tarlatamab. Siltuximab may not be repeated in an individual subject who develops anaphylaxis to siltuximab, or gastrointestinal perforation after siltuximab. As per local institutional guidelines. 	
The next infusion may be administered if all of the following criteria are met:
 
 The medical monitor must be consulted prior to resuming treatment The event has resolved to grade ≤ 1 prior to resuming treatment 
In case of infusion interruption, continue treatment with next scheduled infusion. Do not resume prior infusion or administer delayed infusion.
	
If there is no improvement to CRS \leq grade 2 within 5 days and CRS \leq grade 1 within 7 days.
 
OR
 
If CRS grade 3 occurs at the step dose.
 
OR
 
In the case of 2 separate grade 3 CRS events.

Table 6-2. Tarlatamab Dose Modification Guidelines for Adverse Events

Grade	Description of Severity ^b	Interruption/Delay	Specific Management	Restart guidance	Permanent Discontinuation
Cytokine Release Syndrome continued (see Section 11.11.1 for additional guidance and grading scale details)					
3 (cont.)			
Monitor:
 
 • CRS symptoms including temperature, blood pressure, and pulse oximetry • Fluid status, maintain IVF as needed • Consider chest X-ray and obtaining appropriate cultures to rule out infection • If refractory hypotension (after 2 fluid boluses), consider ECHO 
Admit to intensive care unit for close clinical and vital sign monitoring per institutional guidelines
		
4	
Life-threatening symptoms
 
 • Fever^c: $\geq 38^{\circ}\text{C}$ 
WITH
 
 • Hypotension: requiring multiple vasopressors (excluding vasopressin) 
AND/OR^d
 
 • Hypoxia: requiring positive pressure (eg, CPAP, BiPAP, intubation, and mechanical ventilation) 	Immediately stop any ongoing infusion	
Administer:
 
 • Symptomatic treatment (eg, paracetamol/acetaminophen) for fever • Supplemental oxygen (positive pressure [eg, CPAP, BiPAP, intubation, and mechanical ventilation], as needed) • Multiple vasopressors, as needed • Dexamethasone (or equivalent) IV at a dose maximum of 3 doses of 8 mg (24 mg/d). Further corticosteroid use should be discussed with the medical monitor. • Tocilizumab should be administered at a dose of 4 to 8 mg/kg as a single dose. Tocilizumab can be repeated for an additional 3 doses with at least an 8-hour interval between doses. 	Do not resume tarlatamab	Permanently discontinue tarlatamab

Table 6-2. Tarlatamab Dose Modification Guidelines for Adverse Events

Grade	Description of Severity ^b	Interruption/Delay	Specific Management	Restart guidance	Permanent Discontinuation
Cytokine Release Syndrome continued (see Section 11.11.1 for additional guidance and grading scale details)					
4 (cont.)			
 If tocilizumab is not available, siltuximab (an anti-IL-6 monoclonal antibody) may be used in the management of CRS, following the criteria outlined in this table. The recommended dose of siltuximab is 11 mg/kg administered over 1 hour as an IV infusion, consistent with the prescribing information for the treatment of multicentric Castleman's disease (Sylvant Prescribing Information), and the CARTOX Working Group Guidelines for CRS management (Neelapu et al, 2018). Siltuximab may be repeated if needed, in the event that CRS recurs after a subsequent infusion of tarlatamab. Siltuximab may not be repeated in an individual subject who develops anaphylaxis to siltuximab, or gastrointestinal perforation after siltuximab. 
Monitor:
 
 CRS symptoms including temperature, blood pressure, and pulse oximetry Fluid status, maintain IVF as needed Consider chest X-ray and obtaining appropriate cultures to rule out infection If refractory hypotension (after 2 fluid boluses), consider ECHO 
Admit to intensive care unit for close clinical and vital sign monitoring per institutional guidelines.
		

Table 6-2. Tarlatamab Dose Modification Guidelines for Adverse Events

Grade	Interruption/Delay	Specific Management	Restart guidance	Permanent Discontinuation
Tumor Lysis Syndrome (TLS) (see Section 11.11.3)				
Present	Immediate interruption/delay until event has resolved	TLS should be managed according to the local standard of care and institutional guidelines.	
 Resume only if TLS is successfully managed and resolved in ≤ 14 days Consult with medical monitor first. In case of infusion interruption, continue treatment with next scheduled infusion. Do not resume prior infusion or administer delayed infusion. Monitoring: per Monitoring Guidance for first tarlatamab administration (Section 6.1) 	If subject missed more than 2 consecutive doses of tarlatamab OR In case of repeat TLS event, or life-threatening TLS, permanently discontinue tarlatamab

Abbreviations and footnotes defined on last page of table.

Table 6-2. Tarlatamab Dose Modification Guidelines for Adverse Events

Grade	Interruption/Delay	Specific Management	Restart guidance	Permanent Discontinuation
Non-febrile Neutropenia				
3 ^f	Delay tarlatamab until the event improves to grade ≤ 2	
 Assess for other potential etiologies of neutropenia, including concomitant medications and underlying infection Consider bone marrow biopsy, anti-neutrophil antibodies Granulocyte colony-stimulating factor (G-CSF) administration is permitted 	Resume tarlatamab no less than 72 hours after the initial observation of the grade 3 adverse event	No additional guidance
4 ^f	Delay tarlatamab until the event improves to grade ≤ 2	
 Assess for other potential etiologies of neutropenia, including concomitant medications and underlying infection Consider bone marrow biopsy, anti-neutrophil antibodies Consider G-CSF administration 	Resume tarlatamab no less than 72 hours after the initial observation of the grade 4 adverse event	Initial grade 4 nonfebrile neutropenia event lasts > 7 days OR Grade 4 event reoccurs

Abbreviations and footnotes defined on last page of table.

Table 6-2. Tarlatamab Dose Modification Guidelines for Adverse Events

Grade	Description of Severity	Interruption/Delay	Specific Management	Restart Guidance	Permanent Discontinuation
Hypersensitivity (Allergic Reactions)					
1	Systemic intervention not indicated	No additional guidance	Follow institutional guidelines for management	No additional guidance	No additional guidance
2	Oral intervention indicated	Immediately pause any ongoing infusion	Follow institutional guidelines for management and administer oral antihistamines and/or corticosteroids per local practice.	Restart current infusion of remaining dose at lower rate per local practice if event has resolved	No additional guidance
3	Bronchospasm, hospitalization indicated for clinical sequelae; intravenous intervention indicated	Immediately stop any ongoing infusion and do not resume the current infusion. Delay next tarlatamab administration until the event improves to grade ≤ 1	Follow institutional guidelines for management and administer IV corticosteroids, antihistamines, IV fluids, supplemental oxygen, and consider epinephrine per local practice Close monitoring and Consider ICU transfer	The next infusion may be administered if all the following criteria are met: 
 The Amgen medical monitor must be consulted prior to resuming treatment The event has resolved to grade ≤ 1 prior to resuming treatment Consider premedication (ie, antihistamine, corticosteroid) prior to the next infusion 	Discontinue tarlatamab if: there is no improvement to \leq grade 1 within 5 days OR if grade 3 occurs at the step dose OR in the case of 2 separate grade 3 events.

Table 6-2. Tarlatamab Dose Modification Guidelines for Adverse Events

Grade	Description of Severity	Interruption/Delay	Specific Management	Restart Guidance	Permanent Discontinuation
Hypersensitivity (Allergic Reactions) continued					
4	Life-threatening consequences, urgent intervention indicated	Immediately stop any ongoing infusion and do not resume the current infusion.	Follow institutional guidelines for management and administer epinephrine, IV corticosteroids, antihistamines, IV fluids, and supplemental oxygen per local practice. Immediate medical attention, ICU care, intubation as clinically indicated.	Do not resume tarlatamab.	Permanently discontinue tarlatamab

Abbreviations and footnotes defined on last page of table.

Table 6-2. Tarlatamab Dose Modification Guidelines for Adverse Events

Pituitary Gland Dysfunction (González-Rodríguez and Rodríguez-Abreu, 2016)

 • Monitor for signs and symptoms of pituitary gland dysfunction. Consider the following studies as indicated: TSH, FSH, LH, cortisol, FT4, testosterone/estradiol, ACTH, prolactin, and IGF-1 
 – Abnormal hormone monitoring result or clinical suspicion of pituitary gland dysfunction (headache, fatigue, asthenia, impaired vision, vomiting, hypotension, amenorrhea, impotence) – Diagnostic tests: brain MRI (if clinically indicated), blood pressure, glycemia, plasma and urine osmolality, electrolytes, laboratory values (ACTH, TSH, FSH, LH, IGF-1, plasma cortisol, FT4, prolactin, testosterone/estradiol) • Urgent endocrinology consultation to guide management of the event • Once pituitary gland dysfunction is confirmed, delay scheduled dose of tarlatamab • Once residual related toxicity \leq grade 2, clinically stable on replacement therapy and < 10 mg prednisone or equivalent, resume tarlatamab • Continue endocrinological surveillance
Hepatotoxicity
For Stopping and Rechallenge Rules, please refer to Section 11.7.

Page 12 of 12

ACTH = adrenocorticotrophic hormone; BiPAP = bi-level positive airway pressure; CARTOX = CAR-T-cell therapy-associated TOXicity; CRS = cytokine release syndrome; CPAP = continuous positive airway pressure; ECHO = echocardiogram; FSH = follicle-stimulating hormone; FT4 = free T4; G-CSF = granulocyte colony-stimulating factor; ICANS = immune effector cell-associated neurologic syndrome; IGF-1 = insulin-like growth factor 1; IL-6 = interleukin 6; IV = intravenous; IVF = intravenous fluid(s); LH = luteinizing hormone; MRI = magnetic resonance imaging; OS = overall survival; PS = performance status; TLS = tumor lysis syndrome; TSH = thyroid-stimulating hormone

^a Based on Immune Effector Cells Therapy Toxicity Assessment and Management (also known as CARTOX) <https://www.mdanderson.org/documents/for-physicians/algorithms/clinical-management/clin-management-cytokine-release-web-algorithm.pdf>

^b American Society for Transplantation and Cellular Therapy (ASTCT) grading system for CRS (Lee et al, 2019).

^c Fever is defined as temperature $\geq 38^{\circ}\text{C}$ not attributable to any other cause. In subjects who have CRS then receive antipyretic or anticytokine therapy such as tocilizumab, siltuximab, or steroids, fever is no longer required to grade subsequent CRS severity. In this case, CRS grading is driven by hypotension and/or hypoxia.

^d CRS grade is determined by the more severe event: hypotension or hypoxia not attributable to any other cause. For example, a subject with temperature of 39.5°C , hypotension requiring 1 vasopressor, and hypoxia requiring low-flow nasal cannula is classified as grade 3 CRS.

^e Low-flow nasal cannula is defined as oxygen delivered at ≤ 6 L/minute. Low-flow also includes blow-by oxygen delivery, sometimes used in pediatrics. High-flow nasal cannula is defined as oxygen delivered at > 6 L/minute.

^f For neutropenia adverse events grade ≤ 2 , please follow institutional guidelines for management.

For all other treatment interruptions or delays, restart tarlatamab in accordance with the following guidelines in [Table 6-3](#):

Table 6-3. Step dose Rechallenge Requirement After Tarlatamab Delay

Last Dose Administered	Duration of Delay from the Last Dose Administered	Action
Step dose (1 mg)	≤ 14 days	Proceed with tarlatamab 10 mg target dose and then continue treatment Q2W.
	> 14 days	Repeat tarlatamab 1 mg step dose per cycle 1 guidelines, including pre-medication and monitoring requirements (refer to Table 6-1).
First target dose (10 mg)	≤ 21 days	Proceed with tarlatamab 10 mg target dose and then continue treatment Q2W.
	> 21 days	Repeat tarlatamab 1 mg step dose schedule per cycle 1 guidelines, including pre-medication and monitoring requirements (refer to).
Any subsequent target dose (10 mg)	≤ 28 days	Proceed with tarlatamab 10 mg target dose and then continue treatment Q2W.
	> 28 days	Repeat tarlatamab 1 mg step dose per cycle 1 guidelines, including pre-medication and monitoring requirements (refer to Table 6-1).

Q2W = every 2 weeks.

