Seizure	N/A	N/A	Any clinical seizure focal or generalized that resolves rapidly or nonconvulsive seizures on EEG that resolve with intervention	Life-threatening prolonged seizure (> 5 min); or repetitive clinical or electrical seizures without return to baseline in between
Motor findings ^d	N/A	N/A	N/A	Deep focal motor weakness such as hemiparesis or paraparesis
Elevated ICP/cerebral edema	N/A	N/A	Focal/local edema on neuroimaging ^e	Diffuse cerebral edema on neuroimaging; Decerebrate or decorticate posturing; or Cranial nerve VI palsy; or Papilledema; or Cushing's triad

ASBMT = American Society for Blood and Marrow Transplantation; CTCAE = Common Terminology Criteria for Adverse Events; EEG = electroencephalogram; ICANS = immune-effector cell associated neurologic syndrome; ICE = immune-effector cell-associated encephalopathy; ICP = intracranial pressure;

N/A = not applicable

^a Other signs and symptoms such as headache, tremor, myoclonus, asterixis, and hallucinations may occur and could be attributable to immune effector-cell engaging therapies. Although they are not included in this grading scale, careful attention and directed therapy may be warranted.

^b A subject with an ICE score of 0 may be classified as grade 3 ICANS if awake with global aphasia, but a subject with an ICE score of 0 may be classified as grade 4 ICANS if unarousable.

^c Depressed level of consciousness should be attributable to no other cause (eg, no sedating medication).

^d Tremors and myoclonus associated with immune effector cell therapies may be graded according to CTCAE v5.0, but they do not influence ICANS grading.

^e Intracranial hemorrhage with or without associated edema is not considered a neurotoxicity feature and is excluded from ICANS grading. It may be graded according to CTCAE v5.0.

Source: Lee et al, 2019

Assessment and Supportive Care Recommendations (all grades)

- Neurologic assessment and grading at least twice a day to include cognitive assessment and motor weakness

- MRI of the brain with and without contrast (or brain CT if MRI is not feasible) for \geq grade 2 neurotoxicity
- Neurology consultation at first sign of neurotoxicity
- Conduct electroencephalogram (EEG) for seizure activity for \geq grade 2 neurotoxicity
- Aspiration precautions; IV hydration
- Use caution when prescribing medications that can cause central nervous system (CNS) depression (aside from those needed for seizure prophylaxis/treatment)

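### Table 6-2's ungraded Seizure row overlaps its grade 4 neurologic row, so a first prolonged or repetitive ICANS seizure meets both a permanent stop and a restart pathway, with no precedence stated

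*Protocol*

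**What the plan says.** The neurologic block of Protocol Table 6-2 takes its grades from elsewhere: "Reference Section 11.11.2 for grading and management guidelines". In Table 11-7 of that section, the seizure domain has entries at grades 3 and 4 only; grades 1 and 2 are marked not applicable. Grade 4 is "Life-threatening prolonged seizure (> 5 min); or repetitive clinical or electrical seizures without return to baseline in between". Grade 3 covers seizures that resolve rapidly, or on EEG with intervention.

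Three rows of Table 6-2 can then bear on a seizure:

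- **Grade 3 row.** Delay until grade 1 or less. Restart: "Resume tarlatamab no less than 72 hours after the initial observation of the grade 3 adverse event". There are two grounds for a permanent stop. One is recurrence: "Grade 3 neurologic event reoccurs within 7 days of resuming tarlatamab". The other is lack of timely improvement: "Initial grade 3 neurologic event does not improve to grade ≤ 1 within 7 days".
- **Grade 4 row.** Stop any ongoing infusion. The restart cell and the permanent-discontinuation cell both say "Permanently discontinue".
- **Seizure row.** No grade is given. Delay until grade 1 or less. Restart: "Do not resume tarlatamab until 7 days after the last seizure and after therapeutic levels of anti-seizure medication are likely to have been achieved". Permanent stop: "If a second seizure occurs after resuming tarlatamab".

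The footnotes to Table 6-2 neither rank these rows nor limit the Seizure row to a grade or cause.

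**The concern.** A seizure attributed to ICANS cannot be graded below 3 in Table 11-7, so it always has a numbered row in Table 6-2 as well as the Seizure row. If the two rows agreed, the overlap would not matter. At grade 4 they point in different directions: one ends treatment at the first event, and the other describes the conditions for giving the drug again after a first seizure.

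What is at stake is mainly subject safety. An investigator facing an event that the protocol itself calls life-threatening has to decide between stopping and re-dosing, and the table gives no rule for choosing the row. The table also offers little backstop. It requires the medical monitor to be consulted before resuming after grade 3 CRS, tumor lysis syndrome or grade 3 hypersensitivity, but not in the neurologic or Seizure rows.

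The effect on the data is secondary. SAP Section 9.6.2 summarizes interruption and discontinuation for ICANS and neurological events of interest, and those counts could partly reflect which row a site read.

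**Working it through.** The plan states no figure on this point, so there is none to reproduce. The check sets the rows side by side for each seizure grade.

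| Seizure attributed to ICANS | Numbered row | Seizure row | Can both be followed? |
|---|---|---|---|
| First, grade 4 | Permanent stop | Resumption contemplated after 7 days; its own stop trigger not met | Only by stopping; the Seizure row's restart pathway then has no use at grade 4 |
| Grade 3, restart | At least 72 hours from first observation | At least 7 days from last seizure | Yes, by waiting for the later |
| Grade 3, recurrence | Stop if within 7 days of resuming | Stop at any time after resuming | Yes, the triggers add |
| Grade 3, no improvement in 7 days | Stop | No such trigger | Yes, if both rows apply |

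**Grade 4.** If the more specific row displaces the graded one, resumption is open after a first grade 4 seizure. If all rows apply together, treatment ends. Both are ordinary ways to read such a table, the protocol states neither, and the outcomes are opposite.

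**Grade 3, minimum wait.** 72 hours / 24 = 3 days. For a single seizure, where first observation and last seizure coincide, the difference is 7 − 3 = 4 days. If the last seizure comes k days after the first observation, the difference is (k + 7) − 3 = k + 4 days.

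**Grade 3, next scheduled dose.** Let g be the days between doses and s the day of a single seizure after the earlier dose. The next dose passes the 72-hour test but fails the 7-day test when 3 ≤ g − s < 7.

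- C1D1 to C1D8, and C1D8 to C1D15: g = 7, so s = 1 to 4.
- Every-2-week dosing: g = 14, so s = 8 to 11.

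This counts whole days, ignores visit windows, and assumes improvement to grade 1 or less by the dose date.

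**Grade 3, recurrence.** A seizure on day 3 or 7 after resuming triggers both rows. One on day 10 or 30 triggers only the Seizure row.

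**Scope.** Section 11.11.2 grades ICANS on findings with no other cause. A seizure explained by, say, a brain metastasis would not be graded by Table 11-7. The Seizure row does not say whether it is for these seizures, for ICANS seizures, or for both. Its delay condition, improvement to grade 1 or less, also has no matching entry in the seizure domain of Table 11-7.

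**The case against.** The strongest defense is that the rows can be read together. The grade 4 instruction is unconditional. The Seizure row's restart cell is a prohibition that sets necessary conditions; it does not order re-dosing, and it does not say that a second seizure is the only ground for stopping. On that reading a site that stops breaches nothing, and a site that re-doses after a grade 4 seizure breaches an explicit instruction. A reader might therefore infer too much in saying that two sites could act in opposite ways and both comply: re-dosing complies only if the Seizure row replaces the graded row, and the protocol does not say that it does. This part of the defense stands, but it does not supply the missing precedence rule. The Seizure row names no grade and plainly contemplates resumption after a first seizure.

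A reader might also infer that every seizure meets contradictory instructions. The documents do not support that. At grade 3 both waits are minimums and the stopping triggers are additive. Seizures with another cause lie outside ICANS grading, and they are foreseeable because exclusion criterion 202 admits some subjects with brain metastases. It could be argued that the row was written for these. But it does not say so, it sits in the same block as the graded rows, and a footnote to Table 6-1 lists seizure among ICANS-related neurologic events.

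**Conclusion.** The point holds for grade 4. A first prolonged or repetitive seizure attributed to ICANS falls under a permanent stop and, in the adjacent row, under a restart pathway, with neither scope nor precedence stated. For grade 3 there is an ambiguity in clock start, length and recurrence window, but no contradiction. For seizures with another cause, the Seizure row's coverage is simply unstated.

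This rests on taking Table 11-7 as the grading source, as Table 6-2 directs, and on the Seizure row carrying no grade limit, as printed.

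The importance is for safety and uniform conduct. A reader might attach a statistical size to it, since one subject in 30 is 1/30 = 3.3 percentage points. That figure would hold for any single event in this trial, and the documents give no seizure frequency from which to say how many cases to expect. Safety summaries are descriptive, no hypothesis is tested, and no sample-size or primary-endpoint figure depends on the point.

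**What to change.** Reconcile the Seizure row of Table 6-2 with the grade 3 and grade 4 neurologic rows and with Table 11-7. The revised text should state:

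1. which seizures the Seizure row covers: those attributed to ICANS, those with another cause, or both;
2. which grades it covers, and what improvement to grade 1 or less means for a seizure;
3. which row takes precedence when a graded row and the Seizure row both apply, including which clock and which recurrence window hold at grade 3.

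The clinical team decides which rule holds; this review takes no position on that. The cost is a clarification letter to sites now and a wording change in the next amendment. No analysis, sample size or data collection has to change.
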